Patients with asymptomatic low volume locoregional recurrent disease will be allowed to enroll on this study after discussion with the PI. In the case where the low volume recurrence is amenable to SBRT, it will be included in the SBRT treatment. In the case where the low volume recurrence is not amenable to SBRT based on reirradiation risk, then we will follow these lesions with re-imaging scans and reassess at later time points for further local control, which will be allowed on study. Additionally, if these patients fail only at the untreated site (due to the untreated recurrence/disease not being amenable to SBRT) they will be censored in the primary efficacy analysis at that time. Patients with high risk disease in which salvage radiation to the prostate bed is recommended in the absence of lesions noted on scans will be allowed to enroll after discussion with the PI. In these cases, salvage radiation to the prostate bed may occur at the same time as the SBRT.

Radium Ra 223 dichloride will be administered during ADT therapy based on the knowledge of general synergy between ADT and radiation therapies in the treatment of prostate cancer. Radium Ra 223 dichloride has been developed as a treatment given concurrently with ADT therefore safety of that combination has been established. The purpose of radium Ra 223 dichloride therapy is to enhance anticancer effect against known oligo bone metastases required for eligibility for this study, but also treatment of likely invisible bone micrometastases. Laboratory tests will be monitored every 4 weeks and general guidelines for administration of Radium 223 will be followed. These include: for the 1st dose of Radium 223 baseline laboratory test need to be: Hgb \geq 9.0 g/dL, ANC \geq 1,500 cells/mm³, platelets \geq 100,000 cells/mm³. For subsequent infusions (2-6) there is no Hgb requirement, ANC \geq 1,000 cells/mm³, platelets \geq 50,000 cells/mm³.

Up to 7 cycles of protocol therapy are planned in the absence of unacceptable toxicity or disease progression, whichever comes first. If one agent is discontinued due to toxicity, then the participant may continue to receive the other protocol therapy agent(s).

In addition to capturing efficacy endpoints, participants will undergo follow-up up to 5 years to capture long term toxicities (e.g. secondary malignancies) due SBRT and/or radium Ra 223 dichloride.

Efficacy

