7.6 Radium Ra 223 dichloride

7.6.1 Radiation exposure:

In general, administration of radioactive drugs involves a potential risk for third parties because of radiation from the participant and possible contamination by spilling urine or feces. When radium Ra 223 dichloride has been injected intravenously into a participant, the risk for external radiation exposure to third parties is extremely low, because of the short range of the α particles ($<100\ \mu\text{m}$) and the low portion of β and γ radiation. For these reasons, the product can be administered on an out-patient basis.

To minimize the risk of contamination, participants and his caregivers will receive oral and written instructions regarding hygiene precautions to abide by after receiving radium Ra 223 dichloride.

7.6.2 Side-effects:

The expected toxicities for radium Ra 223 dichloride are as follows (no asterisk signifies $\geq 10\%$; * signifies 1-10%, and † signifies $<1\%$):

Blood and lymphatic (including hematological labs)	Anemia, lymphocytopenia, leukopenia, thrombocytopenia, neutropenia
Gastrointestinal	Nausea, diarrhea, vomiting
General Disorders and Administration Site	Peripheral edema, injection site reaction*
Metabolism and Nutrition	Dehydration*
Neoplasms benign, malignant and unspecified (incl cysts and polyps)	Treatment related secondary malignancy†
Renal and urinary	Renal failure and impairment*

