8.0 DATA & SAFETY MONITORING, ADVERSE EVENT AND UNANTICIPATED PROBLEM REPORTING

8.1 COH Data and Safety Monitoring Plan

Definition of Risk Level

This is a Risk Level 3 study as defined in the [City of Hope Institutional Data and Safety Monitoring Plan](#). This determination was made because this study was deemed IND exempt by the FDA.

Monitoring and Personnel Responsible for Monitoring

The Protocol Management Team (PMT) is responsible for monitoring the data and safety of this study. The PMT consists of the Principal Investigator (PI), Biostatistician, Research Protocol Nurse, and Clinical Research Coordinator.

The PMT is required to submit periodic status reports (i.e., the PMT Report) according to the frequency prescribed in the [City of Hope Institutional Data and Safety Monitoring Plan](#). Important decisions made during PMT meetings (i.e., dose de-escalation, etc.) only need to be noted in the PMT Report submitted to the Data and Safety Monitoring Committee (DSMC).

Adverse Events and Serious Adverse Events

The PI or their designee will be responsible for determining the event name, assessing the severity (i.e., grade), expectedness, and attribution of all adverse events.

Adverse Event (AE) - An adverse event is any untoward medical experience or change of an existing condition that occurs during or after treatment, whether or not it is considered to be related to the protocol intervention.

Reporting Non-serious Adverse Events – Adverse events will be collected after the patient is given the study treatment or any study related procedures. Adverse events will be monitored by the PMT. Adverse events that do not meet the criteria of serious OR are not unanticipated problems will be reported only in the PMT Report.

Serious Adverse Event (SAE) [Modified from the definition of unexpected adverse drug experience in [21 CFR 312.32](#)] - defined as *any expected or unexpected adverse events* that result in any of the following outcomes:

- Death
- Is life-threatening experience (places the subject at immediate risk of death from the event as it occurred)
- Unplanned hospitalization (equal to or greater than 24 hours) or prolongation of existing hospitalization
- A persistent or significant disability/incapacity
- A congenital anomaly/birth defect
- Secondary malignancy

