- Any other adverse event that, based upon appropriate medical judgment, may jeopardize the subject's health and may require medical or surgical intervention to prevent one of the outcomes listed above (examples of such events include allergic bronchospasm requiring intensive treatment in the emergency room or at home, blood dyscrasias or convulsions that do not result in inpatient hospitalization, or the development of drug dependency or drug abuse).

Reporting Serious Adverse Events - begins after study treatment or any study related procedures. All SAEs occurring during this study, whether observed by the physician, nurse, or reported by the patient, will be reported according to the approved [City of Hope's Institutional policy](#). Serious Adverse Events that require expedited reporting will be submitted electronically using [iRIS](#).

Adverse Event Name and Severity

The PI will determine the adverse event name and severity (grade) by using the most current CTCAE version 5.0.

Expected Adverse Event - Any event that does not meet the criteria for an unexpected event, OR is an expected natural progression of any underlying disease, disorder, condition, or predisposed risk factor of the research participant experiencing the adverse event.

Unexpected Adverse Event [21 CFR 312.32 (a)] – An adverse event is unexpected if it is not listed in the investigator's brochure and/or package insert; is not listed at the specificity or severity that has been observed; is not consistent with the risk information described in the protocol and/or consent; is not an expected natural progression of any underlying disease, disorder, condition, or predisposed risk factor of the research participant experiencing the adverse event.

Adverse Event Attribution

The following definitions will be used to determine the causality (attribution) of the event to the study agent or study procedure.

- **Definite** - The AE is clearly related to the investigational agent or study procedure and unrelated to any other cause.
- **Probable** - The AE is likely related to the investigational agent or study procedure and unlikely related to other cause(s).
- **Possible** -The AE may be related to the investigational agent or study procedure and may be related to another cause(s).
- **Unlikely** -The AE is doubtfully related to the investigational agent or study procedure and likely related to another cause(s).

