- e. *Cycle 1 Day 1*: With the exception of PSA, serum testosterone and blood counts other screening evaluations performed within 14 days prior to Cycle 1 Day 1 of protocol therapy may serve as Day 1 baseline evaluations.
- f. Participants must meet criteria in [Section 6.1](#) to initiate SBRT on Cycle 1 Day 1.
- g. Assessments must be performed **within 7 days** prior to radium Ra 223 dichloride. Safety assessments must be reviewed within 7 days prior to initiating a new cycle.
- h. *Cycle 2 Day 1 (1st dose of radium Ra 223 dichloride)*: Participants must meet criteria in [Section 6.2](#).
- i. *Post Ra-223/EOT visit to occur approx. 28 days +/- 7 days post-last dose of Ra 223 dichloride*.
- j. *Response follow-up* assessments for participants yet to progress, will occur ~ every 3 months (± 4 wks) (except [tumor evaluations](#)) from the day of last response evaluation until progression or the initiation of a new therapy.
- k. *Long-term follow-up* assessments for participants who progressed or ended Response Follow-up to occur annually (± 30 days) or as requested by the Study PI via medical record review, review of social security registry/ public records, and/or telephone call.
- l. *Informed consent* process to be fully documented (see [Section 17.4](#)). Informed consent must occur prior to any research only (non-SOC) screening procedures.
- m. *Medical history* to include a review of treatment history, any ongoing medical conditions and medical history pertaining to eligibility on study and involvement during study.
- n. *Eligibility criteria* are detailed in [Section 3.0](#).
- o. *Registration* into a COH clinical trial management system (CTMS).
- p. *Standard physical exam* includes weight and skin analysis.
- q. *Vital signs*: heart rate, blood pressure, respiration rate, and temperature.
- r. *Concurrent medications* and reason for administration to be documented in the EHR and eCRF from within 56 days prior to protocol therapy up to EOT visit. See [Section 5.11.1](#) for concomitant medication restrictions and guidelines.
- s. *Adverse event (AE)* will be assessed using CTCAE v.5.0.
- t. Active AE reporting will start from start of treatment until the post RA-223 visit/EOT visit **NOTE**: The highest AE grade per cycle will be reported in the eCRF from start of therapy until the EOT visit. **Exceptions to expedited reporting** are stated in [Section 8.2](#)

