- u. Long-term toxicities -- secondary malignancy, thyroid dysfunction-- attributed to protocol therapy will be collected via medical record review and/or phone call during Response Follow-up, standard of care visits and Long-term Follow-up. **NOTE**: If the participant is no longer at COH, the study team will request relevant medical information from the external institution.
- v. If clinically indicated by history of cardiovascular disease.
- w. *Serum chemistry* panel to include: glucose, Blood Urea Nitrogen (BUN), creatinine, total protein, albumin, magnesium, bicarbonate, calcium, sodium, potassium, chloride, total bilirubin, alkaline phosphatase, ALT and AST.
- x. *Immune biomarker studies*: Collect 20 mL per timepoint in sodium heparin green-top tubes and store on ice until delivery to [name] laboratory (See [Section 10.2](#) for details). **NOTE**: Notification to the [name]'s laboratory of pending sample collection must be made **at least 1 day in advance** (see [Section 10.2.1](#) for details).
- y. *Tumor tissue*: If available, archival metastatic or primary tissue will be submitted for clinical testing. Refer to [Section 10.1](#) for additional details.

- z. *Fresh metastatic tissue (optional)*: If the participant is willing attempts should be made to take extra metastatic tissue for clinical testing at the time of standard of care biopsy. See also [Section 10.1](#).
- aa. *Tumor Evaluation*: Options include combination of: CT chest, abdomen, pelvis, CXR, targeted X-rays, bone scan, Whole Body MRI, MRI of the TLS spine, MRI of the pelvis, PET/CT. All anatomical areas of the body need to be included (chest, abdomen, pelvis, skeleton) using combination of these tests. Follow up scans should at the minimum include the same scans utilized for screening.
- bb. Tumor evaluation to occur every 6 months (\pm 14 days) from last tumor evaluation, and at PSA progression (unless taken within the last 4 weeks).
- cc. Refer to [Section 5.3](#) for the treatment plan. Refer to [Section 6.3](#) for dose modification/ delay guidelines and [Section 5.9](#) for supportive care guidelines.

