12.2 Toxicity

Toxicity will be graded according to the NCI [CTCAE version 5.0](#). The highest AE grade per cycle will be reported in the eCRF from start of therapy until the end of treatment visit.

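### Footnote u of the study calendar makes attribution to protocol therapy a condition of collecting second cancers in follow-up, rather than a field recorded for each one

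*Combined protocol and SAP*

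**What the plan says.** Assessing long-term toxicity over 5 years of follow-up, in patients who received at least one radium dose, is a secondary objective (section 1.2). Section 2.6 describes the purpose of that follow-up as "to capture long term toxicities (e.g. secondary malignancies) due SBRT and/or radium Ra 223 dichloride".

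The rules on what is collected are these:

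- **Up to EOT.** Footnote t of section 11.0 says "Active AE reporting will start from start of treatment until the post RA-223 visit/EOT visit". Section 12.2 agrees: "The highest AE grade per cycle will be reported in the eCRF from start of therapy until the end of treatment visit".
- **After EOT.** In the adverse event row of Table 11.0, both follow-up columns carry only footnote u: "Long-term toxicities -- secondary malignancy, thyroid dysfunction-- attributed to protocol therapy will be collected via medical record review and/or phone call". Footnote s names the grading system, and footnote k sets the timing and route of long-term follow-up. Neither says which toxicities to collect.
- **Safety definitions.** Section 8.1 defines an adverse event as one "that occurs during or after treatment, whether or not it is considered to be related to the protocol intervention". It lists "Secondary malignancy" among the SAE outcomes without an attribution condition. On reporting it says "All SAEs occurring during this study, whether observed by the physician, nurse, or reported by the patient, will be reported according to the approved" institutional policy, which is not part of the document. It makes the principal investigator or designee responsible for the attribution of every adverse event, on a five-level scale.
- **Special monitoring.** Section 5.5.1 asks staff to watch for osteosarcoma and other second neoplasms, with no attribution limit.

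**The concern.** Sections 8.1 and 5.5.1 treat a second cancer as something to be noted whatever its cause, and 8.1 then has its cause rated. Footnote u reverses the order: someone must first judge the cancer to be attributed to protocol therapy, and only then does the routine follow-up ask for it.

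That matters because secondary malignancy is the example section 2.6 gives for the 5-year toxicity objective, and there is no control arm against which to check the attribution of a single new cancer. If attribution is a recorded field, a reader can re-examine it. If it is a condition of entry, a case judged unattributed need leave no trace in the routine follow-up data. Section 7.5 adds a reason why an assessor might rate an in-window cancer as unlikely to be related: it says radiation-related malignancies usually appear ten or more years after treatment, while follow-up ends at 5. With very few cases expected, one such judgement could change a reported count from 1 to 0.

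**Working it through.** The plan gives no figure of its own to reproduce. The check has two parts.

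**1. Texts side by side**

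| Place | Scope after EOT | Attribution |
|---|---|---|
| 11.0, footnote u | Secondary malignancy, thyroid dysfunction | Condition of collection |
| 8.1, adverse event definition | During or after treatment | Not a condition |
| 8.1, SAE list and reporting | Secondary malignancy listed; no end date stated | Not a condition |
| 8.1, responsibilities | All adverse events | Assessed for each |
| 5.5.1 | Second neoplasms | Not mentioned |
| 2.6 and 7.6.2 | Long-term toxicity; side-effect list | Worded as treatment-related |

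Footnote u is narrower than 8.1 and 5.5.1 and in line with 2.6 and 7.6.2.

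**2. Size**

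Inputs:

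- N = 24 evaluable patients (section 13.3).
- p = risk of a treatment-related second malignancy. Section 7.6.2 marks it as below 1% for radium. That is not a 5-year figure and does not cover SBRT. I use 1% as a ceiling and 0.5% as a lower illustration.
- a = share of such cases that the assessor attributes to treatment. The documents give nothing here; 25% to 75% is an assumption.

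Expected treatment-related cases at the ceiling: 24 × 0.01 = 0.24.

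Chance of at least one treatment-related case, 1 − (1 − p)^24:

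- p = 0.01: 1 − 0.99^24 = 0.214
- p = 0.005: 1 − 0.995^24 = 0.113

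Chance that footnote u leaves out at least one such case, 1 − (1 − p(1 − a))^24:

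| p | a | Result |
|---|---|---|
| 0.01 | 0.75 | 1 − 0.9975^24 = 0.058 |
| 0.01 | 0.50 | 1 − 0.995^24 = 0.113 |
| 0.01 | 0.25 | 1 − 0.9925^24 = 0.165 |
| 0.005 | 0.50 | 1 − 0.9975^24 = 0.058 |

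These are chances that footnote u would not require a case, not that the trial would never learn of it. For radiation-induced cancers they are loose ceilings, because the latency stated in section 7.5 is at least twice the follow-up period.

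Cost of recording everything: if the 5-year risk of any new cancer were 5% to 10% (an assumption, not in the documents), the count would be 24 × 0.05 = 1.2 to 24 × 0.10 = 2.4. That is 5 to 10 times the 0.24 above.

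Precision either way, as exact two-sided 95% intervals: 0/24 gives 0 to 14.2%; 1/24 gives 0.1% to 21.1%.

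**The case against.** The strongest reply is that section 8.1 already covers these events. Secondary malignancy is an SAE whatever its cause, SAE reporting has no stated end date, and attribution is assessed for every adverse event. Footnote t ends only active reporting, and Table 14.3 sets no EOT cut-off for adverse event forms. This stands in part. A reader might infer that unattributed second cancers will be missing from the data for the objective. The documents do not support that: they do not say which dataset feeds the objective, and neither the case report forms nor the SAE policy is supplied. What remains is that footnote u, the instruction for the planned chart reviews and calls, does not ask for such cases.

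A reader might also infer a flat contradiction between footnote u and 8.1. That goes too far, because 2.6 is worded in terms of toxicity caused by the treatment and 7.6.2 lists "Treatment related secondary malignancy". The narrower scope has a basis in the plan.

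Nor is the absence of an attribution level in footnote u a separate defect. The stopping rule in 13.4 and the unanticipated-problem definition in 8.1 both use possible or higher, and that is the natural reading here.

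Finally, collecting all cancers would add mostly background cases, and the attributed subset would still be an investigator's judgement. Both are true. The gain is that the judgement becomes visible, not that it becomes verifiable.

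**Conclusion.** The point holds as a minor, inexpensive improvement. Footnote u filters second cancers by attribution at the point of collection, out of step with 8.1 and 5.5.1, so the routine count for one component of one secondary objective depends on a judgement that a single-arm trial cannot check. At most 0.24 treatment-related cases are expected at the 1% ceiling, and probably fewer within 5 years. The chance that at least one falls outside the routine rule is roughly 0.06 to 0.17 at that ceiling. That range rests on the assumed attributed shares and on applying a radium frequency of unstated duration to 24 patients. A reader might take 0.21 as the 5-year probability of a treatment-related second cancer in this trial; the documents do not support that, since the 1% is neither a 5-year nor an SBRT figure.

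**What to change.** Reword footnote u so that every new primary malignancy is recorded, regardless of attribution, at the chart reviews and calls already planned. Add attribution on the 8.1 five-level scale as a separate field. Report the 5-year count twice, each with an exact interval: all cases, and cases rated possible or higher. State how many patients died or were lost before 5 years, because follow-up is incomplete for them and a crude proportion of 24 ignores that.

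The cost is one case report form item and one wording change. A few background cancers would also be recorded (about 1 to 2 under the assumed 5% to 10% risk). The all-cause total does not isolate a treatment effect and should be labelled accordingly. The attributed count that the present wording aims at remains available as a subset.

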12.0 ENDPOINT EVALUATION CRITERIA/MEASUREMENT OF EFFECT

12.1 Efficacy Endpoints

Response and progression will be evaluated in this study using modified Prostate Cancer Working Group 2 criteria [43] (see [Appendix C](#) and [Appendix D](#)). PSA levels will be a part of overall response assessment. Other clinical efficacy endpoints are described in [Table 12.1](#).

Table 12.1 Efficacy Endpoints

Endpoint	Definition
Time to treatment failure (TTF)	Time from the initiation of ADT for metastatic disease until PSA increase to > pre-ADT level or PSA >10 (whichever is smaller) or radiographic or clinical progression or resumption of ADT by physician's choice
Objective response rate (ORR)	Proportion of patients achieving CR or PR at Cycle 8 Day 1 (post-6 doses of radium Ra 223 dichloride)
Complete response (CR) rate	Proportion of patients achieving CR
Progression-free survival (PFS)	Time from the initiation of ADT for metastatic disease until PSA progression or radiographic progression or death
Bone specific progression-free survival (Bs-PFS)	Time to progression of bone specific disease over baseline
Duration of response (DOR)	Time from documented response to recurrent or progressive disease is first met
Duration of overall complete response	Time from documented CR to recurrent/ progressive disease
Duration of stable disease	Time from start of treatment until the criteria for progression are met, taking as reference the smallest measurements recorded since the treatment started.
Overall Survival (OS)	Date of initiation of protocol treatment to date of death from any cause

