1.0 OBJECTIVES

1.1 Primary Objectives

- To assess the time to treatment failure (TTF) in patients who initiated the protocol regimen of androgen deprivation therapy (ADT) with stereotactic body radiation therapy (SBRT) and radium Ra 223 dichloride and received at least one dose with radium Ra 223 dichloride.

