- Note: patients with asymptomatic low volume locoregional recurrent disease will be allowed to enroll on this study after discussion with the PI. In the case where the low volume recurrence is amenable to SBRT, it will be included in the SBRT treatment. In the case where the low volume recurrence is not amenable to SBRT based on reirradiation risk, then we will follow these lesions with re-imaging scans and reassess at later time points for further local control. Additionally, if these patients fail only at the untreated site (due to the untreated recurrence/disease not being amenable to SBRT) they will be censored in the primary efficacy analysis at that time.

__12. Does not have castration resistant disease

- Castration resistance defined as progression of disease despite serum testosterone level of <50 ng/dL

__13. PSA \geq 0.2 prior to start of androgen deprivation treatment

PSA value:

Date:

__14. Patients will be receiving approximately 36 weeks of ADT as part of this trial. The 36 weeks of ADT may start prior to consenting to this study. The patient may join the study at any point of the 36-week period of ADT treatment.

- Only Luteinizing hormone-releasing hormone (LHRH) agonist/antagonist treatment is considered ADT; bicalutamide or other antiandrogens used alone do not count.

Patient MRN	Patient Initials (F, M, L):
-------------	-----------------------------

___15. Patients must be willing to receive bisphosphonate or RANKL inhibitor bone health agents at the dose and schedule consistent with the treatment of bone metastases or prevention of osteoporosis, starting approximately from when the patient begins protocol therapy, until the patient's testosterone reaches normal levels or at the discretion of the PI. Patients who are already on a bone health agent separate from the protocol may continue on this treatment regimen and will not be required to start treatment with an additional bone health agent.

___16. Patients may have received prior hormone therapy at the discretion of the PI. Patients may have received prior targeted therapy in the context of definitive therapy.

___17. Patients may have had one prior systemic non-chemotherapeutic treatment (i.e. immunotherapy, receptor tyrosine kinase inhibitor, antiangiogenic agent, differentiating agent) for recurrent or metastatic disease.

___18. Must have refused standard of care treatment for metastatic disease

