5.4 Agent Administration

5.4.1 Androgen deprivation therapy

Luteinizing hormone-releasing hormone (LHRH) agonists consisting of either leuprolide OR goserelin OR LHRH antagonist degarelix OR relugolix will be administered per package insert and investigator discretion.

Participants will receive in total 36 weeks of therapy with a LHRH agonist/antagonist; starting at least 28 days prior to initiating Cycle 1 Day 1 stereotactic body radiation therapy.

There is no requirement that the same LHRH agonist/antagonist (whether leuprolide or goserelin or degarelix or relugolix) be administered for the duration of the study.

Dose delay guidelines are described in [Section 6.3](#).

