6.1 Criteria to START SBRT (Cycle 1 Day 1)

Table 6.1 details criteria participants must meet to initiate SBRT.

Table 6.1 Cycle 1 Day 1 SBRT Administration Criteria

Criteria to be met in order to START SBRT	Action if criterion to the RIGHT is NOT met
1. ANC $\geq 1,500/\text{mm}^3$ NOTE: Growth factor support is not permitted to normalize baseline ANC parameters, however subsequent growth factor administration is permitted as standard supportive care.	Permanently discontinue protocol therapy if unable to initiate SBRT 28 (+ 7) days post-1 st dose of ADT (time constraint exception is in patients who started ADT concurrent with radiation tx or surgery). ADT may continue as a non-protocol therapy if clinically indicated.
2. Platelets $\geq 100,000/\text{mm}^3$ *	
3. Hgb $\geq 9.0 \text{ g/dL}$ *	
*NOTE: Transfusion of blood products are not allowed to normalize baseline blood parameters, however subsequent transfusions are allowed per standard supportive care guidelines.	
4. Not experienced \geq recurrent Grade 3 ADT-related AE	Permanently discontinue protocol therapy.
5. ADT related AEs \leq Grade 2	Permanently discontinue protocol therapy if unable to initiate SBRT 28 (+7) days post-1 st dose of ADT (time constraint exception is in patients who started ADT concurrent with radiation tx or surgery). ADT may continue as non-protocol therapy if clinically indicated.
6. Absence of toxicity not present at baseline that might adversely affect participation or results in a reasonable delay prior to initiating SBRT	Permanently discontinue protocol therapy. ADT may continue as non-protocol therapy if clinically indicated.

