13.2 Evaluable Participants

- **Evaluable for toxicity**
 - Patients who received at least 1 SBRT dose will be evaluable for toxicity.
 - Patients who have received at least 1 dose of SBRT and at least 1 dose of Radium 223 will be evaluable for assessment of toxicity and efficacy.
- **Evaluable for response**
 - Only those patients who have evaluable disease present at baseline, have received at least one dose of SBRT and at least 1 dose of radium Ra 223 dichloride, will be considered evaluable for response.

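### TTF runs from ADT start but counts only patients who later receive radium, so earlier failures drop out and the estimate can shift only in the regimen's favour

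*Combined protocol and SAP*

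**What the plan says.** - **Clock.** Table 12.1 in section 12.1: "Time from the initiation of ADT for metastatic disease until PSA increase", or radiographic or clinical progression, or resumption of ADT.
- **Entry.** Inclusion 14 in section 3.1: "The 36 weeks of ADT may start prior to consenting to this study", and "The patient may join the study at any point of the 36-week period of ADT treatment".
- **Who counts.** The primary objective (1.1) covers patients who "received at least one dose with radium Ra 223 dichloride". Section 13.2 asks for "at least 1 dose of SBRT and at least 1 dose of Radium 223 will be evaluable for assessment of toxicity and efficacy". Section 13.3 raises accrual to 25 to obtain 24 evaluable patients after one was inevaluable; the reason is not given.
- **What counts as failure.** Section 13.5 lists radiographic or PSA progression, death, and stopping treatment for clinical progression or toxicity.
- **Earliest radium.** ADT is given "starting at least 28 days prior to initiating Cycle 1 Day 1 stereotactic body radiation therapy" (5.4.1), and Cycle 1, the SBRT cycle, lasts 28 days (5.2).
- **Decision rule.** Section 13.5 compares an observed median with a critical value of 25 months, against a historical 16 months. It describes no delayed-entry or landmark method and no analysis from another time origin.

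**The concern.** A patient becomes evaluable by reaching the first radium dose, yet the TTF clock has been running since ADT began. Time between those two dates is failure-free by selection. Progression at castrate testosterone bars entry (Inclusion 12) or ends protocol therapy (5.6). Tables 6.1 and 6.2 also stop patients before radium for toxicity. Such patients are failures under section 13.5 but are not efficacy-evaluable under section 13.2, and further patients can be accrued in their place.

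This is immortal-time selection. Dropping early failures and keeping the others' full time can raise the TTF curve but cannot lower it. In a 24-patient single-arm study whose only comparator is a historical median, clock and counted set bear directly on the conclusion, and nothing planned would let a reader judge the effect.

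**Working it through.** **1. The plan's own figures.** Inputs from 13.5: 24 patients, 16 months' accrual, 18 months' follow-up, medians 16 and 32 months, one-sided 10%. No distribution is stated; I assume exponential. With λ = ln 2/32 = 0.02166, expected events under the alternative are 24 × [1 − e^(−18λ)(1 − e^(−16λ))/(16λ)] = 24 × (1 − 0.6771 × 0.8451) = 10.27.
- Log-hazard test: critical median = 16 × exp(1.2816/√10.27) = 23.9 months; power = Φ(ln(32/23.87) × √10.27) = 82.6%.
- A cube-root-hazard test gives 24.6 months and 81.2%.

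The stated power above 80% and critical value of 25 both reproduce.

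**2. Built-in lead from ADT start to first radium.**
- Planned minimum: 28 + 28 = 56 days = 8 weeks = 1.84 months, which is 1.84/9 = 20% of the 9-month gain sought. (The calendar's ±7-day cycle window could trim a week.)
- Table 6.1 window plus the full Table 6.2 delay: 35 + 28 + 28 = 91 days = 13 weeks = 3.0 months.
- Inclusion 14 read literally, with SBRT at ADT week 36: 36 + 4 = 40 weeks = 9.2 months.

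**3. Shift in the median.** Suppose the all-comer median from ADT start is 16 months, with hazard f × h during the 36 ADT weeks (8.28 months) and h afterwards. Then f·h·8.28 + h·(16 − 8.28) = ln 2. For patients failure-free at lead L (up to 8.28 months), the median from ADT start is 16 + f·L. The values of f are assumptions.

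| Lead | f = 0 | f = 0.25 | f = 0.5 | f = 1 (constant hazard) |
|---|---|---|---|---|
| 8 weeks | 16.0 | 16.5 | 16.9 | 17.8 |
| 36 weeks | 16.0 | 18.1 | 20.1 | 24.3 |

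**4. Chance that the observed median reaches 25 months when the true median is 16.** Simulation: 24 evaluable patients, uniform accrual over 66 months (13.3), 18 months' minimum follow-up, pre-radium failures dropped, Kaplan-Meier median. Ranges in the f = 1 column cover repeated runs.

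| Lead | f = 1 | f = 0.5 | f = 0.25 |
|---|---|---|---|
| None | 4% | 1% | 0.5% |
| 8 weeks for all | 6-7% | 2% | 0.6% |
| Uniform, 8 weeks to 5 months | 10-11% | 2% | 0.8% |
| Uniform, 8 to 40 weeks | 19% | 4% | 0.9% |

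The 16 + 18-month schedule in 13.5 gives 5%, 8%, 12% and 20% at f = 1. With f = 0 within the ADT course nobody is dropped and nothing changes.

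**5. Entry timing.** The sixth radium dose falls 4 + 5 × 4 = 24 weeks after SBRT starts. All six doses lie inside 36 weeks of ADT only if SBRT starts by ADT week 12.

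**The case against.** The strongest reply is that early failure should be rare. A PSA failure needs a rise above the pre-ADT level or 10, whichever is smaller, while 90% of the predecessor cohort reached a nadir below 0.2 (2.1). Resumption of ADT cannot occur during the ADT course. Progression under continued ADT is put at a median of 14 to 30 months (2.2). No scan is scheduled between screening and the post-radium visit. Table 6.1 also limits the lead when a start criterion is unmet: therapy stops "if unable to initiate SBRT 28 (+ 7) days" after the first ADT dose. All of this stands, and it is why the lower-hazard columns deserve as much weight as f = 1.

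It does not remove the point. Stops for toxicity before radium need no progression. The Table 6.1 limit is waived when ADT began with radiation or surgery, and Inclusion 10 allows ADT to begin with definitive prostate radiation. Section 2.6 says patients often arrive already on ADT.

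A reader might infer that a patient entering at ADT week 36 would have a median of 16 + 9.2 = 25.2 months, meeting the threshold with no radium effect. That needs constant hazard from the first ADT day, entry that Table 6.1 contests, and a 16-month benchmark that excludes the lead. The documents establish none of these. A reader might also quote larger error rates from a 22-month cut-off calibrated to 10%; the protocol's criterion is 25 months.

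**Conclusion.** The point holds as a one-directional selection bias of unknown size. It should be fixed, but it does not invalidate the design. At the 8-week minimum, the chance of passing at a true median of 16 stays below the stated 10% even under constant hazard. It clearly exceeds 10% only if hazard is constant and entry is spread out to about 40 weeks. With ADT-period hazard at half the later hazard or less, it stays at or below about 5% in every entry pattern examined.

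Two unknowns decide the matter: the failure rate before radium, and the time origin and population of the 16-month benchmark. If that benchmark also runs from ADT start and early failure is rare, the comparison is nearly unaffected. Section 13.5 also counts stopping for toxicity and death as failure, whereas Table 12.1 lists neither, so which pre-radium exits are lost depends on the definition used.

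**What to change.** Keep TTF from ADT start as the primary endpoint and add to section 13.5:

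1. A supportive TTF analysis of every patient who received at least one SBRT fraction, counting pre-radium failures as events under one stated failure definition.
2. A sensitivity analysis with delayed entry at first radium, reporting median TTF from first radium and the distribution of the ADT-to-radium interval. A delayed-entry curve alone is not enough, because on the planned schedule nobody is at risk in the first 8 weeks.
3. The time origin and population of the 16-month benchmark, so that the comparison with 25 months uses the same clock.

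A test with the clock moved to first radium should not become primary. Against a constant 16-month hazard, its type I error falls to 1.4% or less, against a nominal 10%, in the lower-hazard cases.

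The cost is SAP wording; the dates are already collected. The supportive medians will probably be somewhat shorter.

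Separately, the entry-timing passages must be reconciled: Inclusion 14 (any point of the ADT course), Table 6.1 (28 + 7 days, with its exception), 5.4.1 (at least 28 days) and 2.6 ("Radium Ra 223 dichloride will be administered during ADT therapy based on the knowledge of general synergy"). No clinical rule is proposed here.
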